15.3 Training of Staff

Each individual involved in this trial should be qualified by education, training, and experience to perform his or her respective tasks.

Site staff may be trained for this study at investigator meetings and initiation visits by MCRI, or their designees.

The PI will maintain a record of all staff involved in the trial at each site. The PI will ensure that appropriate training relevant to the trial is given to all these staff, and that they will receive any new information relevant to the performance of this trial.

15.4 Changes to the Protocol

Trial procedures will not be changed without the agreement of MCRI.

If it is necessary for the trial protocol to be amended, the amended protocol must be approved by the IEC, unless the immediate safety of participants is involved.

If a protocol amendment requires a change to the PICF, approval of the revised PICF by MCRI or their designee and by the IEC is required before the revised form can be used.

MCRI or their designee will distribute amendments and new versions of the protocol to the PI. The PI will be responsible for submitting to the IEC.

MCRI or their designee will also distribute amendments and new versions of the protocol to the regulatory agencies. Regulatory approval must be obtained prior to implementation.

15.5 Trial Agreements

The PI and site coordinating investigator at each centre must comply with all the terms, conditions and obligations of the trial agreement for this trial. In the event of any inconsistency between this protocol and the trial agreement, the trial agreement shall prevail.

15.6 Trial Timetable and Termination

The planned start date for this trial is mid to late-2017. The proposed completion date is in 2019.

MCRI reserves the right to terminate the trial at any stage for any reason including commercial considerations. In the event of early termination, MCRI and designees will work with the PI and site staff to ensure all participants are appropriately discontinued and follow up for safety.

15.7 Ethics and regulatory review

The protocol, PICF, and other patient-facing documents will be submitted for approval to the IEC and regulatory agency, and must be approved or given a favourable opinion in writing as appropriate. The investigator must submit written approval to MCRI or designee before they can commence recruitment or enrol any participants into the trial.

Any amendment to the protocol will be sent to the IEC and regulatory agency. No deviations from or changes to the protocol will be implemented without documented

approval/favourable opinion from the IEC and regulatory agency of an amendment, except where necessary to eliminate an immediate hazard to a trial participant, or when the changes involve only logistical or administrative aspects of the trial.

The deviations from or changes to the protocol which were implemented to eliminate an immediate hazard to a trial participant and the proposed amendment, if appropriate, should be submitted to the IEC and regulatory agency for review and approval as soon as possible.

The PI must submit progress reports to the IEC according to local regulations and guidelines. The PI must also provide the IEC with any reports of SAEs from the trial site in accordance with the IEC requirements and timelines.

MCRI or designee will report to the regulatory agency as required.

15.8 Ethical Conduct of the Trial

The trial will be performed in accordance with the ethical principles in the Guidelines of the World Medical Association's Declaration of Helsinki in its revised edition (Fortaleza, Brazil, October 2013), ICH GCP, the approved study protocol, and applicable regulatory requirements.

15.9 Insurance and Liability

Liability and insurance for this study are addressed in the Clinical Trial Agreement. MCRI will not, under any circumstances, have any responsibility or liability regarding any injury to, or death of, an infant or infant's mother arising from or in connection with delivery or birth of a potential research participant.

15.10 Participant Information and Consent

The investigator at each centre will ensure that the participant's parents/guardians are given full and adequate oral and written information about the nature, purpose, possible risk and benefit of the trial prior to obtaining both preliminary and final study consent. Parents/guardians must also be notified that they are free to discontinue their child from the trial at any time. The parents/guardians should be given the opportunity to ask questions and should be allowed time to consider the information provided.

The participant's parents/guardians' signed and dated informed consent must be obtained before conducting any procedure specifically for the trial. The PI must store the original, signed PICFs. A copy of the signed and dated PICFs must be given to the parents/guardians.

15.11 Data Protection

The PICF will explain that trial data will be stored in a computer database, maintaining confidentiality of participants. Participants in this database will be identified by Screening and Randomisation Number only. The PICF will also explain that for data verification purposes, authorised representatives of MCRI or their designees, regulatory authorities, IECs or sites may require direct access to parts of the hospital or site records relevant to the trial, including the participant's and mother's personal information.

15.12 Archiving

The PI is responsible for the archiving of the trial records for their site. Trial records include the participant files as well as the source data, the Investigator Site File, pharmacy records, and other study documents. Trial records must be archived for at least 15 years (or at least 2 years after the formal discontinuation of clinical development of RV3-BB vaccine).

However, these documents should be retained for a longer period if specified by regulatory requirements or by an agreement with MCRI. It is the responsibility of MCRI to inform the PI/institution as to when these documents no longer need to be retained. Records may not be destroyed without prior written consent from MCRI.

If the PI leaves the investigational site for any reason, the responsibility for all study related records must be transferred to another person at site.

15.13 Emergency Procedures

The PI is responsible for ensuring that procedures and expertise are available to cope with medical emergencies during the trial.

If emergency unblinding is required, the site should contact the study Medical Monitor. Contact details are provided in the SRM.

15.14 Publication Policy

The publication policy for the study will be specified in a separate contract(s) between MCRI, and other relevant parties involved with the clinical study.

17 APPENDICES

17.1 Appendix 1: Modified Vesikari Grading Scale for Gastroenteritis in Children

Non severe diarrhoea < 11 points

Severe diarrhoea ≥ 11 points

Points Value Symptom	1	2	3
Duration of diarrhoea (days)	1-4	5	≥6
Max. number of diarrhoea stools/24hrs	1-3	4-5	≥6
Duration of vomiting (days)	1	2-4	≥5
Max. number of vomiting episodes/24hrs	1	2-5	≥6
Temperature (degrees C)*	37.1 - 38.4	38.5 - 38.9	≥39.0
Dehydration	-	Some (1-5%)	Severe (≥6%)
Treatment	Rehydration	Hospitalisation	-

Reference: (Ruuska ,1990)

*Temperature measurements will be entered into the CRF as axillary measurements and converted at the database level to rectal equivalent temperatures, which are standard for Vesikari scoring.

Modifications

Children who receive oral rehydration solution prior to the dehydration assessment AND who have at least one of the signs of "some" dehydration according to the Integrated Management of Childhood Illness dehydration criteria at the initial clinic assessment receive a score of 2 for 'Dehydration'

Use of NG, IV or six hours of supervised oral rehydration is scored as hospitalisation (score of 2) for 'Treatment'

Reference:

Lewis, K. Vesikari Clinical Severity Scoring System Manual. Seattle: PATH; Version 1.3, 2 May 2011.

SD	Standard deviation
SOC	System organ class
TLFs	Tables, data listings and figures

1. Overview

1.1.1 Introduction

This document describes the rules and conventions to be used in the presentation and analysis of a phase II randomised, double blind, parallel group dose-ranging study of oral RV3-BB Rotavirus Vaccine administered at a titre of 1×10^7 , 3×10^6 or 1×10^6 as a 3 dose neonate schedule or administered at a titre of 1×10^7 as a 3 dose infant schedule.

This statistical analysis plan (SAP), is based on protocol MCRI-RV3-BB-004, version 04, dated 11-Jan-2019 and CRF, Version 05, Dated 22-Jul-2019.

2. Trial objectives

The following objectives are those stated in the protocol.

2.1.1 *Primary objectives*

The primary objective of this study is to assess a cumulative anti-rotavirus serum IgA response (defined as a \geq 3-fold increase from baseline) 4 weeks after 3 doses of RV3-BB administered in a neonatal schedule at a vaccine titre of 1x10⁷, 3x10⁶ or 1x10⁶.

2.1.2 Secondary objectives

The secondary objectives of this study are:

- To assess the cumulative anti-rotavirus serum IgA response (defined as a ≥3-fold increase from baseline) 4 weeks after 3 doses of RV3-BB administered in an infant schedule at a vaccine titre of 1x10⁷.
- To assess cumulative vaccine take and components of vaccine take after 3 doses of RV3-BB (titre of 1x10⁷) administered in a neonatal schedule versus three doses of RV3-BB in an infant schedule at a vaccine titre of 1x10⁷.
- To assess cumulative vaccine take and the components of RV3-BB vaccine take after 3 doses of RV3-BB administered as a neonatal schedule at a vaccine titre of 1x10⁷, 3x10⁶ or 1x10⁶.
- To assess cumulative vaccine take and components of vaccine take after 2 doses of RV3-BB administered as a neonatal schedule at a vaccine titre of 1x10⁷, 3x10⁶ or 1x10⁶ or 2 doses as an infant schedule at a vaccine titre of 1x10⁷.
- To assess cumulative vaccine take and components of vaccine take after the first dose of RV3-BB administered as a neonatal schedule at a vaccine titre of 1x10⁷, 3x10⁶ or 1x10⁶ compared to placebo (1st dose of IP in the infant schedule).
- To assess cumulative vaccine take and components of vaccine take after the first dose of RV3-BB at a vaccine titre of 1x10⁷, 3x10⁶ or 1x10⁶ in the neonatal schedule compared with the first dose of RV3-BB at a vaccine titre of 1x10⁷ in the infant schedule.
- To describe the geometric mean titre of the anti-rotavirus serum IgA response after 3 doses of RV3-BB administered as a neonatal schedule or an infant schedule.

- To describe the safety and tolerability of RV3-BB when administered as an infant or as a neonatal schedule.
- To describe the occurrence of diarrhoea episodes in participants, according to severity and detection of wild-type rotavirus.

2.1.3 Exploratory objectives

The basis of the exploratory objectives is to further understand potential barriers to rotavirus vaccine efficacy in the region. The exploratory objectives of this study are:

- To describe Histo-blood Group Antigens (Lewis and Secretor) status of participants in association with anti-rotavirus sero-conversion and cumulative vaccine take after 3 doses RV3-BB administered in either the neonatal schedule (any titre) or infant schedule.
- To assess maternal anti-rotavirus IgA and IgG levels in association with antirotavirus IgA seroconversion and cumulative vaccine take in participants following receipt of RV3-BB administered in either the neonatal schedule (at any vaccine titre) or infant schedule at a vaccine titre of 1x10⁷.
- To describe the gut microbiome in participants receiving RV3-BB administered in the neonatal schedule (at any vaccine titre) or infant schedule at a vaccine titre of 1x10⁷.
- To describe innate and adaptive immune responses in infants vaccinated with RV3-BB administered in the neonatal vaccine schedule (any titre) or in the infant schedule at a vaccine titre of 1x10⁷.

3. Endpoints

3.1.1 Immunogenicity endpoints

Immunogenicity will be assessed through:

- Serum anti-rotavirus IgA response (defined as a ≥3 fold increase from baseline) at each serum collection time-point to 4 weeks after 3 doses of RV3-BB.
- Serum anti-rotavirus IgA levels at each serum collection time point.
- Vaccine take defined as at least a threefold increase in serum anti-rotavirus immunoglobulin A (IgA) from baseline to post IP dosing, or detectable RV3 shedding in stools (by ELISA or PCR) any day from day 3 to 5 following administration of IP.
- Cumulative vaccine take defined as vaccine take observed at the current assessment time point or following any previous dose.
- Anti-rotavirus IgA response (defined as at least a threefold increase from baseline to post IP dosing) at each serum collection time point.
- Presence of RV3 shedding in stools (by ELISA or PCR) from day 3 to 5 following each dose of IP.
- Anti-rotavirus IgA titres defined as geometric mean titres at each serum collection time point.
- Episodes of diarrhoea, from the time of randomisation to 28 days following the last dose of IP. Episodes will be confirmed by Rotavirus antigen ELISA on samples.

3.1.2 Safety and tolerability endpoints

Safety and tolerability will be assessed through:

- Unsolicited Adverse Events (AE) in the days 0-28 following each dose of IP.
- Serious Adverse Events (SAE) from the first dose of IP until 28 days post last dose of IP.
- Review of episodes of blood in stool.

3.1.3 Exploratory endpoints

Exploratory endpoints will be assessed through:

HBGA Lewis and Secretor status will be determined by ELISA/PCR on Saliva samples collected at Visits 1, 3, 5 and 7 and whole blood collected at Visit 9 for non secretor participants.

- Maternal serum IgA and IgG response will be determined on maternal serum sample collected pre study or at Visit 1.
- Bacterial taxonomic and genetic functional profiling of stool microbiome will be conducted on stool samples collected post administration of IP and at birth (prior to first IP dose).
- B and T cell function will be measured by flow cytometry and innate and adaptive responses measured by whole killed pathogen assay and Toll like receptor ligand assays from whole blood collected at birth (cord), Visit 3 and Visit 9.

4. Trial design

4.1.1 Design overview

This is a Phase II, randomised, double blind, four arm parallel group study. Approximately 688 participants will be randomised to the study; 172 to each treatment arm.

Pregnant women will be invited to provide preliminary consent for the study prior to labour and delivery. A maternal blood sample and a stool will be collected. Following delivery, those who remain interested will be invited to provide written informed consent for their baby to participate in the study.

Following confirmation of eligibility for the trial post-birth, participants will be randomised in a 1:1:1:1 ratio to one of four treatment arms; high-dose, mid-dose or low-dose neonatal schedule, or a high-dose infant schedule. Each study participant will receive four oral doses of IP, with each administration consisting of 1 mL RV3-BB Rotavirus Vaccine or 1mL of placebo. All participants will receive a total of 3 doses of RV3-BB vaccine, one dose of placebo, and one dose of Rotarix®.

A baseline stool sample will be collected prior to the administration of the first dose of IP. A stool sample will also be collected on either Day 3, 4 or 5 following each dose of IP. Samples will also be collected for any cases of diarrhoea (defined as 3 or more stools that are looser than normal for that participant).

A saliva sample collected at birth and prior to IP doses 2, 3 and 4.

Cord blood will be collected at birth (or a venous blood sample if cord not available), and blood samples taken prior to IP doses 2, 3 and 4, and prior to the Rotarix® dose.

Participants will be followed until 18 weeks of age. Face to face visits will be conducted at least monthly. Adverse events, including blood-in-stool occurrences, and diarrhoea episodes will be recorded for the duration of the study.

An independent Data Safety Monitoring Board (DSMB) will review safety data at agreed recruitment and progression milestones throughout the study, as agreed and documented in the DSMB Charter. The DSMB will recommend whether the study continues unchanged, continues with amendments, or is stopped. Recruitment will continue during the DSMB review periods.

4.1.2 Study duration

The recruitment period is estimated at 9 months. The study period for each participant will be 18 weeks, and the total duration of the study approximately 15 months.

MCRI-RV3-BB-004

4.1.3 Schedule of Procedures

Visit	Pre-study	1	2	ς,	4	5	9	7	8	99
Timing		Day 1	Day 8	Week 6	Week 7	Week 10	Week 11	Week 14	Week 15	Week 18
Window	Second trimester to birth	Birth to 144 hrs old	7±1 days post V1	+7 days	7±1 days post V3	±7 days and at least 21 days post V3	7±1 days post V5	±7 days and at least 21 days post V5	7±1 days post V7	±7 days and at least 21 days post V7
Preliminary consent	X									
Cord blood collection	Х									
Maternal blood sample	Х									
Maternal stool sample	Х									
Study consent		Х								
Eligibility confirmation		Х								
Demographics and medical history		Х								
Physical exam		Х								
Vital signs ¹		Х	Х	Х	Х	х	Х	х	Х	Х
Stool sample	X_2	X^{6}		X^6		X^6		X^6		
Saliva sample		Х		Х		Х		X		
Randomisation		Х								
IP administration		Х		Х		Х		X		
Antacid administration ²				Х		Х		X		
EPI vaccine administration ⁹		Х		Х		Х		X		Х
IPV administration				Х		Х		X		
Rotarix® administration										\mathbf{X}^7
Pre dose blood sample		X^{10}		Х		Х		Х		Х
Issue/review diarrhoea log ³		Х		Х		Х		Х		Х
Issue/review study reminder Card ³		Х		Х		Х		X		Х
Issue stool sample kits ³		Х		Х		Х		Х		
Feeding review ⁴		Х	Х	Х	Х	Х	Х	Х	Х	Х
AE recording		Х	Х	Х	Х	Х	Х	Х	Х	Х
Con med recording		Х	Х	Х	Х	Х	Х	Х	Х	Х
Follow up contacts				Wee	kly contact (clinic, home o	r telephone)	throughout th	le study	
1. Temperature, pulse rate, respiratory	rate. At dos	ing visits	vital signs v	vill be meas	ured within c	ne hour pre-do	se and 15 a	nd 30 mins po	ost dose.	

CONFIDENTIAL OP-BS-02 v01 TPL-1.0: Statistical Analysis Plan Template

Page 15 of 58

4
0
0
1
മ
ഥ
-1
က
>
Ŕ
 
$\overline{}$
Ľ
C
Ś
~

- 2mL of Mylanta Original® will be administered within the 10 minutes prior to the IP dose.
- Logs, reminder card and kits will be issued and reviewed as required ы м

Record percentage of baby's intake that is breast milk, formula, or other.
 A pre-dose stool sample will be collected at any time before the first dose of IP.
 A stool sample will be collected 3 – 5 days post dose.
 If the participant withdraws prior to receiving all IP doses they will be given a Rotarix® dose one month following their last dose of IP.
 Day 1 pre-dose sample will be cord blood.
 EPI vaccines will be provided via usual supplier (not study) but administered by study staff at appropriate time points according to standard schedule. The exceptions are OPV and other rotavirus vaccines, which will not be given 5.4 of the protocol).
 A 1.0mL blood sample will be collected if cord blood is not able to be collected.

CONFIDENTIAL OP-BS-02 v01 TPL-1.0: Statistical Analysis Plan Template

5. Changes/deviations from the planned analysis

Analysis and reporting of some exploratory objectives of this study will be completed outside of this analysis plan and the clinical study report. The analysis for the immune development and microbiome endpoints will take a significant amount of time to complete and the complex nature and large amounts of data generated for each will impact on the time to reporting for the primary endpoint. The disposition of samples collected specifically for these exploratory objectives will be included as listings in the clinical study report.

This relates specifically to the below objectives and endpoints of the study. For each objective an analysis plan will be pre-defined and documented prior to starting analysis and an addendum report or publication and will be added to the clinical study report when all analysis is complete.

Objectives:

- To describe the gut microbiome in participants receiving RV3-BB administered in the neonatal schedule (at any vaccine titre) or infant schedule at a vaccine titre of 1x10⁷.
- \circ To describe innate and adaptive immune responses in infants vaccinated with RV3-BB administered in the neonatal vaccine schedule (any titre) or in the infant schedule at a vaccine titre of 1x10⁷.

Endpoints:

- Bacterial taxonomic and genetic functional profiling of stool microbiome will be conducted on stool samples collected post administration of IP and at birth (prior to first IP dose).
- B and T cell function will be measured by flow cytometry and innate and adaptive responses measured by whole killed pathogen assay and Toll like receptor ligand assays from whole blood collected at birth (cord), Visit 3 and Visit 9.

Based on established data on cord blood serum IgA in 100 mother baby pairs in Indonesia (Chan et al 2011) and also in New Zealand in the Phase IIa study (77 cord blood tested for serum IgA) (Bines et al 2015) and reported elsewhere, we anticipate that all participants should have a cord blood serum IgA concentration lower than the limit of detection (20 units). This is consistent with biology and if serum IgA is detected in cord blood above the definition of baseline it is not biologically plausible and could be an error at the time of collection or processing of the sample. During sample testing and analysis the laboratory reported that a higher than previously observed rate of collection error for cord samples with approximately 15-20% of samples swapped or contaminated at the time of collection. It has been reported elsewhere that up to 20% of samples are often contaminated or invalid at the time of collection (Tong et al 2002).

In previous studies, samples with an IgA result greater than 30 were excluded from analysis and handled as missing data (assigned a value of 10) (Bines et al 2018). In response to the observation of increased collection/ handling error (in previous studies the total samples excluded based on sampling or collection error was approximately 5%) it is planned to assign all baseline cord values greater than 30 to lower than the limit of detection (assigned a value of 10) for analysis for serum IgA primary and secondary analyses. A sensitivity analysis for the primary analysis using the reported cord values for serum IgA as the baseline value for the calculation of a serum IgA response will also be presented (note, this is only relevant for comparisons involving the neonatal schedule where cord blood is used as the baseline).

6. Analysis populations

Agreement and authorization of participants included/excluded from each analysis population will be reached and documented prior to final database hard lock. TCD will provide the sponsor with a list of all potential participants to be excluded from the relevant analysis populations, including the reason(s) for exclusion from the analysis populations. Decisions about these potential exclusions from specific analysis populations will be made at a Blinded Data Review Meeting [to include at least the sponsor, responsible TCD statistician and the responsible project manager(s)], the minutes of which will document any decisions about exclusions from analysis populations. The Blinded Data Review Meeting will occur prior to database lock to ensure that any final potential queries can be answered before the final lock. Any reclassification/recategorization of protocol deviations during the Blinded Data Review Meeting will be considered final to align with decisions reached on exclusions from analysis populations.

The following sets will be used for the statistical analyses:

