8.1.1 Sample size

With the high titre RV3-BB neonatal vaccine schedule as the active control arm, the sample size is calculated to demonstrate the non-inferiority of the lower titre vaccine arms with respect to the proportion of participants who have a serum IgA response, 4 weeks after 3 doses of vaccine. A non-inferiority margin of 20% for the difference between arms will be used.

The primary analysis is based on the per protocol population defined as participants who receive all 3 doses of RV3-BB and have no major protocol violations. Thirty percent of participants are expected to be excluded from the PP population due to death, study withdrawal, loss to follow-up, or study non-compliance. Among those in the PP population, a 50% response probability is assumed for the active controls. Based on a one-sided 0.025 level score test with 90% power under the alternative of no difference in response probabilities, 172 participants per arm are required for a total sample size of 688 participants.

8.1.2 *Multicentre studies*

Approximately 688 babies will be randomised across three sites in Malawi. Study visits will be conducted at the sites or at participant homes.

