The difference between high and low titre arms in the response rate and its 95% confidence interval will be calculated. The cumulative probability of anti-rotavirus serum IgA response (as defined above) by 18 weeks of age will be estimated by the Kaplan-Meier method for each vaccine arm. PROC LIFETEST (SAS[®] Version 9.4 or above) will

be used to analyse the response rates (non-responder *vs.* responder). With the CENSOR variable, 1 is commonly used to indicate that an event occurred (subject is a responder) and 0 indicates that the event did not occur (the subject was censored/is a non-responder).

Non-inferiority of the lower titre vaccine will be demonstrated if the upper bound of the confidence interval is below 20%.

Additionally, we will calculate the 95% CI of the difference between vaccine groups in the serum IgA response rate after dose 3 using the method of Newcombe-Wilson without continuity correction for the difference between binomial proportions as implemented in PROC FREQ (SAS® Version 9.4 or above).

Generalized estimating equations (GEE) will be used to analyse the response rates (non-responder vs. responder) after dose 3 using PROC GEE (SAS® Version 9.4 or above). We will calculate a binary outcome ($1 = \ge 3$ -fold increase, 0 = < 3-fold increase from baseline) after dose 1, 2, and 3 for each participant who received vaccine according to the neonatal schedule. After that, we will fit a model with dose as a discrete/categorical/factor variable, vaccine group (low, medium, high dose) as a discrete variable, and dose by vaccine group interaction term. The model will use the binomial distribution for the outcome variable and the exchangeable correlation matrix to account for the correlation between a participant who received vaccine according to the neonatal schedule outcomes. Model will be used for the analysis. Once the model is fit, contrast statements will be used in PROC GENMOD (SAS® Version 9.4 or above) to calculate the difference in the response rate after dose 3 for the high versus low dose and so forth.

In the table, (Estimate, standard error, 95% CI) will be presented.

The general linear model to be fit by GEE is

 $logit(p_{ij}) = \beta_{ij}$

where p_{ij} is the response rate after the i-th dose in the j-th vaccine group. Differences between the β s represent the log odds ratio in response rates.

MCRI-RV3-BB-004

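### The one planned check of the cord IgA reset rule leans towards non-inferiority if the SAP's own explanation is right; an analysis excluding the flagged infants is missing

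*SAP*

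**What the plan says.** For the neonatal arms the baseline is cord blood, or a pre-dose venous sample where no cord blood was obtained (SAP 7.1.2). Response is a rise of at least threefold from that baseline (SAP 9.1.1).

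SAP section 5 expects every cord value to be below the detection limit of 20 units. Of a detectable value it says that "it is not biologically plausible and could be an error at the time of collection or processing of the sample". It reports that roughly 15-20% of cord samples were swapped or contaminated, against about 5% excluded for such errors in earlier studies. The primary and secondary analyses therefore set any cord value above 30 to 10, much as earlier trials treated such values as missing. One check is named: "A sensitivity analysis for the primary analysis using the reported cord values for serum IgA as the baseline value".

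SAP 9.1.2 gives the decision rule: "Non-inferiority of the lower titre vaccine will be demonstrated if the upper bound of the confidence interval is below 20" (per cent). SAP 7.1.4 and 9.1.2 also plan ITT, Newcombe-Wilson and GEE analyses of the same endpoint. These change the population or the method, but none changes how a suspect cord baseline is handled. No analysis leaves out the infants concerned.

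**The concern.** A sensitivity analysis should be able to disagree with the primary analysis when the primary is wrong. Here the check restores as baselines the very values that the SAP considers implausible. With the reset, an affected infant needs a post-dose IgA of 30 to respond (3 x 10). With the reported value, the same infant needs 93 if the tube read 31, and 900 if it read, say, 300 (an illustration, not a figure from the documents). Some true responders are then scored as non-responders, in every titre arm alike.

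If the errors are equally common across arms, each arm's response rate is multiplied by the same factor below 1, and so is the difference between arms. In a superiority trial that would be conservative. Under a rule that passes when the upper bound of the difference is below 20 points, it favours passing.

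At stake is how much weight a reader may put on agreement between the two runs. The reset rule may touch about one cord baseline in six, and this is the only check on it.

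**Working it through.** **Inputs from SAP 8.1.1.** "Based on a one-sided 0.025 level score test with 90% power under the alternative of no difference in response probabilities"; "A non-inferiority margin of 20% for the difference between arms will be used"; "a 50% response probability is assumed for the active controls"; "Thirty percent of participants are expected to be excluded from the PP population"; "172 participants per arm are required for a total sample size of 688 participants".

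**Reproducing the plan's figure.** With the simple unpooled formula, n = (1.960 + 1.282)² x (0.5 x 0.5 + 0.5 x 0.5) / 0.20² = 10.51 x 0.50 / 0.04 = 131.3, so 132 evaluable per arm. Then 132 x 1.3 = 171.6, or 172, which matches the plan. (Dividing by 0.7 instead would give 189.) With 30% excluded, 172 x 0.7 = 120 per arm remain in the PP set, and this n is used below. Power under no difference is then 89.0% by exact enumeration.

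**Method.** Two independent binomials are enumerated exactly, and a trial passes if the Newcombe upper 95% bound of high minus low is below 0.20. The truth is set at the margin, 50% versus 30%, so every pass is a false one.

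**As-reported run, if the high values are errors.** Let f be the fraction of infants with a falsely high baseline (0.15 or 0.20, assuming that all the faulty samples read high) and k the share of affected true responders who still respond. Each rate is multiplied by 1 - f + f x k. For f = 0.20 and k = 0 the factor is 0.80: 50% becomes 40%, 30% becomes 24%, and the difference falls from 20 to 16 points.

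| f | k | Apparent rates (%) | Difference (points) | Passes |
|---|---|---|---|---|
| 0 | – | 50.0 v 30.0 | 20.0 | 2.7% |
| 0.15 | 0.75 | 48.1 v 28.9 | 19.3 | 3.5% |
| 0.20 | 0.75 | 47.5 v 28.5 | 19.0 | 3.8% |
| 0.15 | 0.50 | 46.3 v 27.8 | 18.5 | 4.6% |
| 0.20 | 0.50 | 45.0 v 27.0 | 18.0 | 5.5% |
| 0.15 | 0 | 42.5 v 25.5 | 17.0 | 7.9% |
| 0.20 | 0 | 40.0 v 24.0 | 16.0 | 10.8% |

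Wald and score bounds give similar results for k = 0: about 7.0-7.9% at f = 0.15 and 9.8-10.8% at f = 0.20 across the three methods.

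**Primary run, if the high values are real.** If every affected infant keeps a post-dose IgA of at least 30, the reset turns them all into responders, and each rate p becomes p + f(1 - p). For f = 0.15 this gives 0.50 + 0.15 x 0.50 = 57.5% and 0.30 + 0.15 x 0.70 = 40.5%, a difference of 17 points that passes in 7.7% of trials. For f = 0.20 it gives 60% versus 44%, a difference of 16 points that passes in 10.2%.

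**Excluding the flagged infants.** This leaves 120 x 0.85 = 102 or 120 x 0.80 = 96 per arm. At 50% versus 30% it passes in 2.6-2.9% of trials (n = 96, 99 and 102), and power under no difference is about 82%.

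**The case against.** The strongest defence is that the as-reported run tests the right rival hypothesis. The reset was adopted after the laboratory saw an unexpected error rate, and the SAP says only that a high value could be an error. If some are real, the reset creates responders: a stable IgA of 100 would count as a tenfold rise. Using the reported values removes them. This stands, and is why the as-reported run should be kept. It does not remove the gap. If the values are errors the check leans towards non-inferiority, if they are real the primary does, and with a mixture both do in part. Neither planned run is neutral under both explanations.

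The second objection concerns size. The top of the range needs every faulty sample to read high, every affected infant to be scored a non-responder, and a true deficit of exactly 20 points. The SAP does not say that the 15-20% are the samples above 30, and a tube swapped between two newborns could still read below 20. This also stands; the size is an assumed range.

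Third, a reader might infer that an inferior titre becomes three to four times more likely to be declared non-inferior. The documents do not support that. The ratios of about 3 and 4 (7.9/2.7 and 10.8/2.7) belong to the worst case of the sensitivity run, and no section makes that run decisive. If the values are errors, the reset is about right and the primary stays near 2.7%. When both runs are simulated on the same infants, with no affected infant able to respond, both pass in only about 2.3% of trials.

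A reader might also infer that the check distorts the neonatal-versus-infant comparison. SAP section 5 limits it to the primary analysis, which compares titres within the neonatal schedule, and no section clearly plans it for the schedule comparison.

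**Conclusion.** The point holds as a weakness in the robustness check, not as an error in the primary decision. If the SAP's explanation of the high cord values is right, the planned check leans towards non-inferiority. At a true 20-point deficit its pass rate rises from 2.7% to somewhere between about 3.5% and 10.8%. The direction follows from the threefold rule and from errors being equally common across arms; the size rests on an IgA distribution that the documents do not give. If the values are real, the compression moves to the primary analysis, up to 7.7-10.2% in the extreme case. Agreement between the two planned runs is therefore weak support for either.

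The calculation speaks only to deficits at the margin. A titre that is truly 15 points worse lies inside the 20-point margin, so a higher pass rate there would not be a false claim by the trial's own criterion.

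**What to change.** In SAP section 5 and SAP 7.1.4:

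- Add a sensitivity analysis of the primary endpoint that excludes infants whose cord IgA is above 30. The flag rests on a pre-dose sample, so it cannot depend on the assigned vaccine and the randomised comparison is kept. The analysis avoids the compression under either explanation of the high values.
- Keep the as-reported run beside it, with a note that it is biased towards no difference if the high values are errors.
- Report the number of reset cord values by arm, so that a reader can judge whether the errors were equally common.

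The cost is SAP wording and one more run of an existing program. The added analysis uses about 96-102 infants per arm, with about 82% power instead of 89%, which is acceptable for a supporting analysis.
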